
1. Early recognition of patients needing specialist postoperative input
	
Royal College of Anaesthetists: Guidelines for the Provision of Anaesthesia Services 2019²⁵
 
 • Provision of Postoperative Care Recommendation 3.23: Mechanisms for the early recognition of patients requiring specialist postoperative input from geriatrician-led services and/or critical care should be developed. These should include patients at risk of or presenting with delirium, multiple medical complications, functional decline or complex discharge planning.

2. Postoperative intravenous iron therapy is indicated in patients with iron deficiency anaemia
	
International consensus statement on Postoperative Anaemia after Major Surgery 2018²⁶
 
 • Postoperative iron therapy: Should postoperative iron therapy be indicated, i.v. formulations are recommended

3. Extended pharmacological VTE prophylaxis is indicated in patients at high VTE risk after major abdominal or pelvic surgery
	
National Institute of Clinical Excellence: Venous thromboembolism in over 16s: reducing the risk of hospital-acquired deep vein thrombosis or pulmonary embolism (NG89) 2018
 
 • Consider extending pharmacological VTE prophylaxis to 28 days postoperatively for people who have had major cancer surgery in the abdomen.

Methods

1. Summary

A prospective, multicentre, study will be delivered by STARSurg Collaborative & EuroSurg Collaborative across Europe. Mini-teams of up to four collaborators (medical students and at least one doctor) per speciality group per data collection period will prospectively collect data over a continuous 14-day period at each participating centre. This will be on consecutive patients undergoing major abdominal surgery, with follow-up to 30 postoperative days. All mini-teams should be supervised by a consultant in surgery.

2. Study Aims:

- **Primary Aim:** To audit compliance to pre-, intra-, and postoperative audit standards in reducing risk of postoperative cardiovascular complication.

- **Secondary Aims**
 - To characterise rates and risk factors associated with postoperative cardiovascular complications following major abdominal surgery in Europe.
 - To explore the association of pre-operative and postoperative anaemia with postoperative cardiovascular complications and short-term outcomes (length of stay, readmission and 30-day mortality).

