- 30-day reoperation rates
- Critical care bed days up to 30 days postoperatively
- Length of in-patient stay (days) up to 30 days postoperatively
- 30-day readmission rates
- 30-day bleeding event rates (see **Appendix D: Definitions of Key Outcomes**)
- Length of pharmacological VTE prophylaxis (days) up to 30 days postoperatively.

Follow-up should be performed in line with current routine practice within each hospital settings. No additional telephone, in-person or questionnaire-based follow-up is required. Source data may be acquired from hospital in-patient notes, clinical electronic systems, or outpatient letters.

Prior to collecting data, all collaborators will be required complete the mandatory e-learning modules available from the CASCADE project online hub:
<https://incept.ac.uk/course/view.php?id=7>

These include: (1) CASCADE Patient selection; (2) Clavien-Dindo classification (3) Postoperative cardiovascular complications; (4) Postoperative bleeding complications; (5) VTE pharmacological prophylaxis; (6) Data safety governance; (7) Quiz

8. Data Governance:

Data will be collected and stored online through a secure server running the Research Electronic Data Capture (REDCap) web application,^{27,28} and allows safe anonymised data storage by collaborators across Europe. The service is managed by the Birmingham Surgical Trials Consortium (BiSTC) REDCap system hosted at the University of Birmingham, United Kingdom. The security of the study database system is governed by the policies of the University of

Birmingham. Data management and data security within the BiSTC REDCap will abide by the requirements of the General Data Protection Regulations (GDPR) and any subsequent amendments. Collaborators will be given secure REDCap project server login details, allowing secure data storage on the REDCap system.

No patient data will be uploaded or stored on the REDCap database without prior local permissions. All data should be handled in accordance with local data governance policies, and all paper copies of any data should be destroyed as confidential waste within the centre once uploaded to REDCap. Data collected during the CASCADE study can be used for future analyses at the Study Management Group's discretion.

9. Data Analysis & Sample Size:

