Based on previous STARSurg and EuroSurg studies, CASCADE is anticipated to include around 300 centres in Europe. With consideration to recent figures provided by previous STARSurg and EuroSurg studies, it has been estimated that, on average, ten patients will undergo surgery per week at each participating centre. Therefore, a sample of approximately 6000 patients is anticipated. No surgeon-, hospital- or country-specific comparisons will be performed. Further secondary analyses may be performed at the Study Management Group discretion.

10. Local Project Registration:

At European centres, if the option is available, this project may be registered as clinical audit, quality improvement project or service evaluation. Alternatively, it may be necessary to obtain formal ethical approval. It is the responsibility of the local mini-team at each site ensure that the study is registered appropriately, according to local regulations. CASCADE should be registered in the UK and ROI as a clinical audit. It is the responsibility of the local mini-team at each site to identify a local consultants in surgery, anaesthesia or critical care to supervise them and ensure registration.

Confirmation that ethical review is not required for CASCADE within the UK is available in **Appendix F**. Examples of audit registration forms can be found at the online project hub. When registering CASCADE as a clinical audit you can emphasis that:

- CASCADE is a national audit, and all data collected will measure current practice.
- No changes to normal patient pathways/ treatment will be made.
- All CASCADE data will be collected and stored online through a secure server running the

Research Electronic Data Capture (REDCap) web application.²⁸ REDCap allows collaborators to enter and store data in a secure system. Collaborators will be given secure REDCap project server login details, allowing secure data storage on the REDCap database.

Collaborators in the UK should seek their trust's Caldicott Guardian's permission to submit data to the REDCap system. **No data should be uploaded to REDCap prior to written approval from the Caldicott Guardian.** No patient identifiable information (e.g. NHS numbers) should be uploaded or stored on the REDCap database without explicit permission from the trust's Caldicott Guardian. All data should be handled in accordance with national and local data governance policies.

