Appendix D: Definitions of Key Outcomes

A. Cardiovascular complications:

There are several factors which can increase the risk of postoperative cardiovascular complications in the perioperative content, particularly in patients with pre-existing cardiac disease.

There are heterogenous definitions with the medical literature regarding which conditions should be considered postoperative cardiovascular complications (and how these should be defined). This makes it difficult to interpret new studies in the context of the existing literature, and so means it often is not possible to pool the data within systematic reviews.

A recent systematic review and international consensus process¹³ recommended redefining postoperative cardiovascular outcomes that can be used in future trials to measure the effectiveness of perioperative interventions. The following outcomes are included within the new definition of perioperative cardiovascular adverse events:

1. **Atrial fibrillation:** New onset of irregularly irregular heart rate in the absence of P wave lasting at least 30 s or for the duration of the ECG recording (if <30 s)
2. **Myocardial infarction:** Acute myocardial injury with clinical evidence of acute myocardial ischaemia and with detection of an increase or decrease in cardiac troponin (cTn) values with at least one value above the 99th percentile upper reference limit (URL) and at least one of the following:
 - a. Symptoms of myocardial ischaemia
 - b. New ischaemic ECG changes
 - c. Development of pathological Q waves
 - d. Imaging evidence of new loss of viable myocardium or new regional wall motion abnormality in a pattern consistent with an ischaemic aetiology
 - e. Identification of a coronary thrombus by angiography or autopsy - Post-mortem demonstration of acute atherothrombosis in the artery supplying the infarcted myocardium.

Cardiac death in patients with symptoms suggestive of myocardial ischaemia and presumed new ischaemic ECG changes before cTn values become available.

- 3. Myocardial injury:** Detection of an elevated cTn value above the 99th percentile URL is defined as myocardial injury. The injury is considered acute if there is an increase or decrease in cTn values
- a. Note: it is not clinically possible to distinguish which increases of cTn levels are attributable to which mechanisms

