 - b. A diagnosis of myocardial infarction requires an increase of cTn values and evidence of myocardial ischaemia that may be evident from the peri- and postoperative period (e.g. ST segment changes on telemetry/ECG, repeated episodes of hypoxia, hypotension, tachycardia, or imaging evidence of myocardial injury)
 - c. In the absence of evidence for acute myocardial ischaemia, the diagnosis is acute myocardial injury
- 4. Coronary revascularisation:** Cardiac revascularisation procedure was defined as percutaneous coronary intervention or coronary artery bypass graft surgery within 30 days of the index surgery.
- 5. Cardiac death:** Death with a vascular cause and included those deaths after a myocardial infarction, cardiac arrest, and cardiac revascularisation procedure.
- a. Excludes:
 - i. Death after pulmonary embolism
 - ii. Death after haemorrhage
 - iii. Death after multi-organ failure
 - iv. Cause of deaths unknown
- 6. Non-fatal cardiac arrest:** Successful resuscitation from either documented or presumed ventricular fibrillation, sustained ventricular tachycardia, asystole, or pulseless electrical activity requiring cardiopulmonary resuscitation, pharmacological therapy, or cardiac defibrillation
- 7. Major adverse cardiac event:** A composite outcome that should include:
- a. Cardiac death (as defined previously)
 - b. Myocardial infarction (as defined previously)

- c. Non-fatal cardiac arrest (as defined previously)
- d. Coronary revascularisation (as defined previously) within 30 days of index surgery
- e. *Excludes* - Pulmonary embolism, haemorrhage, deep venous thrombosis, all-cause mortality

8. Pulmonary embolism may present as sudden death, breathlessness, faintness, collapse or chest pain. Diagnosis of pulmonary embolism requires any one of following:

- a. A high probability ventilation/perfusion lung scan
- b. An intraluminal filling defect of segmental or larger artery on a helical CT scan
- c. An intraluminal filling defect on pulmonary angiography
- d. A positive diagnostic test for deep venous thrombosis (e.g. positive compression ultrasound) and one of the following:
 - i. Non-diagnostic (i.e. low or intermediate probability) ventilation/perfusion lung scan
 - ii. Non-diagnostic (i.e. sub-segmental defects or technically inadequate study) helical CT scan

9. Deep vein thrombosis (DVT) is defined as the formation of a thrombus (blood clot) in a deep vein.

- a. Diagnosis of DVT requires any one of the following:

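### Whether troponin was measured is not recorded, so myocardial injury rates and risk factors cannot be separated from testing practice; Appendix D also leaves the infarction/injury line ambiguous

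*Protocol*

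**What the plan says.** **Definition of injury.** Protocol Appendix D, A.3: "Detection of an elevated cTn value above the 99th percentile URL is defined as myocardial injury". The next sentence calls the injury acute if troponin rises or falls. A.3c then assigns the label of acute injury whenever ischaemia is not evident, without repeating the rise-or-fall condition.

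**Definition of infarction.** A.2 asks for a rise or a fall in troponin with a value over the limit, plus one item from a list a-e: symptoms, new ischaemic ECG changes, Q waves, imaging evidence, or coronary thrombus. A.3b, a note under the injury heading, says infarction requires an increase in troponin and evidence of ischaemia. Its examples include "repeated episodes of hypoxia, hypotension, tachycardia, or imaging evidence of myocardial injury". Hypoxia, hypotension and tachycardia are not in a-e.

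**MACE.** A.7 includes infarction and leaves injury out.

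**Ascertainment.** Section 7: "Follow-up should be performed in line with current routine practice within each hospital settings". Appendix E repeats that normal follow-up must not change.

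**Data fields.** Appendix B collects cardiovascular complications as a tick list with the postoperative day of each event. Injury has its own box. Troponin does not appear among the blood tests, the preoperative investigations or the postoperative fields, and Appendix A has none either.

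**Use.** A secondary aim in section 2 is "To characterise rates and risk factors associated with postoperative cardiovascular complications following major abdominal surgery in Europe". The primary outcome is compliance with audit standards.

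**The concern.** An endpoint that exists only when a test is ordered measures two things at once: how often the event occurs and how often clinicians look for it. Under routine care, testing will probably vary between hospitals and with the patient's perceived risk. If so, any characteristic that prompts testing will appear to be a risk factor for injury, whether or not it is one.

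This could be handled if testing were recorded, but it is not. No later analysis can recover a field that was never collected. The rule requiring more than 95% data completeness does not help, because an unticked injury box in an untested patient counts as complete.

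The second problem concerns classification. Collectors at many centres will apply Appendix D, and infarction enters MACE while injury does not. Two passages that draw the line differently therefore move patients into or out of MACE depending on which one the collector follows.

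**Working it through.** **1. The plan's own figure.** Section 9 gives "CASCADE is anticipated to include around 300 centres in Europe" and "on average, ten patients will undergo surgery per week at each participating centre", and section 1 sets collection "over a continuous 14-day period at each participating centre". So 300 × 10 × 2 = 6000, which matches "a sample of approximately 6000 patients is anticipated". The protocol states no testing rate for troponin, so every testing share below is an assumption.

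**2. Effect on incidence.** If testing is unrelated to injury, observed incidence = true incidence × share tested. Take a true rate of 25%. This is the upper figure that the Introduction gives for abdominal and pelvic surgery, used here only as an illustration.

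| Share tested (assumed) | Observed rate | Cases in 6000 |
|---|---|---|
| 10% | 0.25 × 0.10 = 2.5% | 150 |
| 20% | 0.25 × 0.20 = 5.0% | 300 |
| 50% | 0.25 × 0.50 = 12.5% | 750 |
| 100% | 25% | 1500 |

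The 95% half-width at 25% is 1.96 × √(0.25 × 0.75 / 6000) = 1.1 percentage points. Testing practice would outweigh sampling error.

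**3. Effect on risk factors.** Let the true rate be p with and without a factor, and let t1 and t0 be the shares tested. The observed risk ratio is (p × t1) / (p × t0) = t1 / t0, whatever p is.

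- 30% v 20% tested: 0.30 / 0.20 = 1.5. With p = 25% the observed rates are 7.5% v 5.0%, odds ratio 1.54. With p = 10% they are 3.0% v 2.0%, odds ratio 1.52.
- 40% v 10% tested: 0.40 / 0.10 = 4.0. With p = 20% the observed rates are 8% v 2%.

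If 30% of the 6000 patients carry the factor (1800 v 4200, assumed), a two-sided 5% comparison of proportions at 30% v 20% tested would call this null factor significant with probability 0.65 (p = 10%) to 0.96 (p = 25%).

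**4. The infarction/injury line, side by side.**

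| Patient, troponin over the limit | A.2 | A.3b-c read as a dividing rule |
|---|---|---|
| Rising troponin; only repeated tachycardia, hypotension or hypoxia | No item of a-e: injury, not MACE | Evidence of ischaemia: infarction, MACE |
| Falling troponin; ischaemic symptoms | Infarction, MACE | No increase: infarction requirement not met |

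To show the scale, assume 5% of 6000 are troponin-positive (300) and 1% meet A.2 (60). Of the other 240, assume 10% to 50% show only hypoxia, hypotension or tachycardia, which is 24 to 120 patients. Infarctions number 60 under A.2 and 84 to 180 under A.3b-c. Every extra infarction also meets the MACE definition.

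**5. Chronic elevation.** A.3 makes any value over the limit injury and reserves rise or fall for the label acute. The tick-box does not say acute, and no rise-or-fall field or preoperative troponin exists. A long-standing raised value can therefore be ticked and cannot be identified afterwards.

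**The case against.** A reader might infer that cardiovascular incidence, MACE and the risk-factor results as a whole are uninterpretable. The documents do not support that. Atrial fibrillation, pulmonary embolism, deep vein thrombosis, stroke, cardiac arrest and revascularisation are defined without troponin. Injury is not part of MACE, and three of the four MACE components (cardiac death, non-fatal arrest, revascularisation) need no troponin. A.2 also provides for cardiac death before a troponin result is available. The benchmark promised in the Introduction concerns composite endpoints, and the only composite that Appendix D names leaves injury out. The primary outcome is not touched.

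One could also say that A.2 and A.3b flatly contradict each other. That is too strong. A.3b says what infarction requires, and a necessary condition is not a sufficient one. Item 2 is the headed definition, and A.7 refers back to infarction as already defined. But A.3c assigns the remainder to injury, so the two notes together work as a second dividing line, and nothing says which governs. An ambiguity remains.

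Other objections have force. An audit may not alter care, and clinically detected injury is a meaningful quantity if labelled as such. Injury has its own box, so it can be dropped in analysis, possibly under an SAP not seen here. The testing shares are not from the protocol. The 25% is an upper bound whose cited source, by its title, concerns emergency surgery, while this cohort includes elective patients.

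None of this removes the gap. Recording whether a test was done changes no care, and dropping injury does not make its own rate interpretable. The protocol already separates symptomatic from asymptomatic clots, but does nothing comparable for troponin.

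**Conclusion.** The point holds in a limited form. Incidence and risk factors for myocardial injury, and for any composite that includes it, cannot be separated from who was tested, and the recorded fields do not allow correction. The spurious risk ratio equals the ratio of testing shares: 1.5 at 30% v 20% and 4.0 at 40% v 10%. These rest on assumed shares and equal true risk, and show the mechanism rather than predict its size.

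Infarction and hence MACE counts depend on how a collector reads A.2 beside A.3b-c. How many patients this moves is unknown; the 60 v 84 to 180 range is illustrative.

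The missing test field does not affect the complications defined without troponin, the three MACE components that need none, or the primary compliance outcome. The change is worth making because a stated secondary aim is affected and the missing information cannot be recovered later.

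**What to change.** - Add two items to the postoperative form in Appendices A and B: *postoperative troponin measured: yes / no*, and *rise or fall shown: yes / no / single value*.
- Report injury among tested patients, always beside the proportion tested. Label any rate over all patients as clinically detected injury.
- Report risk-factor results for cardiovascular complications with and without troponin-only injury.
- Reconcile A.2 with A.3b-c so that one stated rule separates infarction from injury for data collectors. The definitions come from an external consensus, so the authors should check them against that source; this review does not say which passage should prevail.

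The cost is two tick-boxes, an edit to Appendix D, and fewer events in the analysis without troponin-only injury. No extra testing or follow-up is needed.

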2. Critical care bed days (if yes)	Number (days from first post-operative day to day of discharge from critical care. If the patient has not been discharged prior to the end of 30-day follow-up, enter '31').	
3. Postoperative haemoglobin	Not applicable / Available (day 0-1, day 1-3, day 4-6, last prior to discharge) If available, please state value in grams/litre	
4. Postoperative interventions for anaemia	None / iron supplementation / Tranexamic acid / RBC transfusion (If yes: 1, 2, 3, 4, ≥5 units)	
5. Cardiovascular complications within 30 days	None / Myocardial infarction / Myocardial injury / Non-fatal cardiac arrest / Coronary revascularisation / Pulmonary embolism (symptomatic non-fatal / asymptomatic) / Deep venous thrombosis (proximal / distal; if either symptomatic / asymptomatic) / New onset Atrial fibrillation / Stroke (select all that apply) *see Appendix D for definitions Please indicate the POD of the event(s) selected.	• Clinical notes • PACS software
6. Bleeding complications within 30 days	None / Major bleeding / Clinically relevant non-major bleeding *see Appendix D for definitions	
7. Post-operative length of stay	Number (days between from the first post-operative day to day of discharge. If the patient has not been discharged prior to the end of 30-day follow-up, enter '31').	
8. Highest 30-day complication grade	None / Clavien-Dindo Grade I-V (see Appendix D for the full 7-point Clavien-Dindo scale). If grade V, was death cardiac, PE or non-cardiac? (see Appendix D for definitions)	
9. 30-day Reoperation	Yes / No	
10. 30-day Readmission	Yes - planned / Yes- unplanned / No (this applies if patient had died during initial admission) If yes: what is the grade of complication (none, grade I, grade II, grade III, grade IV, grade V)	
11. 30-day postoperative COVID status	None / Preoperative / Postoperative If preoperative: are you still symptomatic (yes/no) and were you vaccinated (no / partial / full)	
12. Haemoglobin on readmission	Not available / Available If available, please state value in grams/litre	
13. Interventions for anaemia at readmission	None / iron supplementation (Oral / Intravenous), blood transfusion (If yes: 1, 2, 3, 4, ≥5 units)	
14. Postoperative outpatient VTE prophylaxis duration	Number (days of pharmacological VTE prophylaxis the patient was discharged home with)	

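### The protocol's definition of cardiac death takes in some non-cardiac vascular deaths, and the cause-of-death field cannot show which ones

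*Protocol*

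**What the plan says.** Appendix D, A.5 of the protocol defines cardiac death as "Death with a vascular cause and included those deaths after a myocardial infarction, cardiac arrest, and cardiac revascularisation procedure". Four exclusions follow: "Death after pulmonary embolism", "Death after haemorrhage", "Death after multi-organ failure" and "Cause of deaths unknown".

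Appendix D, A.7 builds the MACE composite from four components. The first is "Cardiac death (as defined previously"); the others are myocardial infarction, non-fatal cardiac arrest and coronary revascularisation. Its own exclusion line reads "Pulmonary embolism, haemorrhage, deep venous thrombosis, all-cause mortality". Stroke is neither a component nor on that line. It is a separate outcome (A.10) with its own tick item.

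Cause of death is collected once, under the highest 30-day complication grade (Appendix B, post-operative item 8): "If grade V, was death cardiac, PE or non-cardiac". The item refers to Appendix D for definitions. The summary form in Appendix A carries the same three options. Neither place has a free-text cause of death or an option for unknown cause.

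**The concern.** The label and the definition point in different directions. The label says cardiac. The definition is vascular, and the three cardiac antecedents it names are given as included cases, not as limits. The separate exclusion of pulmonary embolism supports that reading, because it would hardly be needed if only coronary deaths qualified.

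A collector who goes by the label will code a fatal ischaemic stroke as non-cardiac. One who applies A.5 will code it as cardiac. The collectors are student-led teams at about 300 centres, and the protocol describes no central adjudication of cause of death. The cohort includes emergency bowel resection and open aortic surgery, so deaths from visceral or limb ischaemia are plausible.

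What is at stake is the fatal component of MACE. The Introduction gives benchmarking of the new composite cardiovascular endpoints as a reason for the study. A component that depends on whether the collector followed the label or the definition serves that aim less well. Under the literal definition, MACE also counts a fatal ischaemic stroke while leaving out a non-fatal one.

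**Working it through.** **Step 1: the planning figure.** Methods section 9 expects about 300 centres and ten patients per centre per week; each collection period lasts 14 days. With one period per centre, 300 × 10 × 2 = 6000, which reproduces the stated sample. It is used below only to give a scale.

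**Step 2: types of death, read against A.5 and against the plain label.**

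| Death | A.5 read literally | Plain label | Can it be re-sorted later? |
|---|---|---|---|
| After myocardial infarction | Cardiac, in MACE | Cardiac | Not needed |
| After pulmonary embolism | Excluded | PE | Not needed |
| Ischaemic stroke | Cardiac, in MACE | Non-cardiac | Partly, from the stroke tick |
| Haemorrhagic stroke | Can fall under the haemorrhage exclusion | Non-cardiac | Partly; the tick has no subtype |
| Visceral or limb ischaemia, no multi-organ failure | Cardiac, in MACE | Non-cardiac | No |
| Visceral ischaemia through multi-organ failure | Excluded | Non-cardiac | Not needed |
| Unknown cause | Excluded | No matching option | No |

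Label and definition clearly disagree in two rows: ischaemic stroke, and visceral or limb ischaemia without multi-organ failure. Both groups reach MACE only through its cardiac-death component.

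**Step 3: what can be recovered.** The stroke tick (Appendix B, post-operative item 5) is not limited to non-fatal events, and the dictionary asks for the postoperative day. A grade V record with stroke ticked can therefore be flagged. The tick does not separate ischaemic from haemorrhagic stroke, although the haemorrhage exclusion may turn on that, and it does not show that the stroke caused the death. Visceral and limb ischaemia have no field at all.

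**Step 4: size.** The documents give no rate for MACE or for vascular death, so the effect cannot be computed from them. The following is an illustration on assumed rates only.

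- MACE counted narrowly: assumed 1% to 3% of 6000, or 60 to 180 events.
- Non-cardiac vascular deaths that meet A.5: assumed 0.05% to 0.2% of 6000, or 3 to 12 deaths.
- Relative rise in MACE if all of them are coded as cardiac = extra deaths ÷ MACE events.

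| Assumed MACE | 3 deaths | 6 deaths | 12 deaths |
|---|---|---|---|
| 60 (1%) | 5.0% | 10.0% | 20.0% |
| 120 (2%) | 2.5% | 5.0% | 10.0% |
| 180 (3%) | 1.7% | 3.3% | 6.7% |

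In absolute terms the MACE rate moves by 3/6000 to 12/6000, or 0.05 to 0.2 percentage points. Each cell compares every team following A.5 with every team following the label. Mixed practice would fall between the two.

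**The case against.** The best defence is that the field is not ambiguous on paper. Item 8 sends the collector to Appendix D, so the coding that conforms to the protocol is the A.5 one. Collectors must also pass e-learning that includes a module on postoperative cardiovascular complications, with a 100% pass mark. In addition, the protocol presents its definitions as those of a consensus initiative, adopted so that results can be compared. Most of this stands. What remains is a foreseeable coding risk, because the option label itself suggests the other answer.

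Several stronger readings are tempting but are not supported:

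- **Every vascular death counts as cardiac.** The four exclusions prevent this. They can remove fatal haemorrhagic stroke, and they remove visceral-ischaemia deaths that pass through multi-organ failure.
- **MACE excludes stroke by name.** It does not. Stroke is omitted from the components, and a non-fatal stroke is still counted as a cardiovascular outcome of its own.
- **The form contradicts the definition.** The pointer to Appendix D rules that out; the fault is a mismatch between label and definition.
- **The affected deaths can never be separated.** This is true of visceral and limb ischaemia, but only partly true of stroke.
- **The distortion of MACE is large.** A reader could assume 2% to 3% mortality (120 to 180 deaths), 5% to 15% of deaths from non-cardiac vascular causes (6 to 27 deaths) and 60 to 120 MACE, and reach 6/120 = 5% to 27/60 = 45%. No such rate is in the documents. The upper end pairs the highest death count with the lowest MACE count, and the calculation does not net off the exclusions.
- **MACE should be redefined to the narrow count.** That would replace wording the protocol presents as consensus. Whether A.5 matches its source cannot be checked here.

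**Conclusion.** The point holds in a limited form. A.5 is wider than its label, some non-cardiac vascular deaths enter MACE on a literal reading, and the three-option field invites inconsistent coding that later analysis can repair only in part. Missing information on cause of death cannot be supplied by an analysis plan.

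The size cannot be computed from the documents and is probably small. On the assumed rates above it is a fraction of a percentage point in absolute terms, or 1.7% to 20% relative to the MACE count. That range rests wholly on the assumed rates.

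Reach is also limited. The primary outcome is audit compliance. Methods section 7 names the incidence of cardiovascular complications as a secondary outcome and does not name MACE. This is a cheap improvement, not a threat to the study's main result.

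**What to change.** Split the cause of death in Appendix B, post-operative item 8, and in the Appendix A form, into five options: cardiac; PE; other vascular (stroke, visceral or limb ischaemia); non-vascular; unknown. The unknown option is needed because A.5 excludes such deaths but the form has no place for them.

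Add one sentence to A.5 stating which of these categories make up cardiac death, with the four exclusions still applying. Keep the A.5 wording as the MACE component so that comparability is preserved. Report the narrower, cardiac-only count beside it as a sensitivity figure.

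The cost is a few extra drop-down options shown only for deaths, one sentence in Appendix D and one extra reported figure.
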